9.3 Populations for Analyses

The following populations are defined:

Population	Description						
Enrolled	All participants who sign the ICF						
Full analysis set	All participants randomized who have received at least 1 dose of study intervention. Participants will be analyzed according to the intervention they were randomized.						
Safety analysis set	All participants randomly assigned to study intervention and who took at least 1 dose of study intervention. Participants will be analyzed according to the intervention they received.						
Pharmacokinetic set	All LICA-treated participants with at least 1 PK sample in accordance with the PK sampling schedule (Section 8.5) and without deviation from the protocol that would interfere with the evaluation of the PK data will be included in the PK analysis.						
Pharmacodynamic set	All participants with at least 1 PD sample in accordance with the PD sampling schedule and without deviation from the protocol that would interfere with the evaluation of the PD data will be included in the PD analysis.						
Listing only set	All participants who signed consent but are not randomized.						

9.4 Statistical Analyses

The statistical analysis plan will be finalized prior to database lock and it will include a more technical and detailed description of the statistical analyses described in this section. This section is a summary of the planned statistical analyses of the most important endpoints including primary and key secondary endpoints.

For the primary analysis: an unblinded data snapshot will be conducted after all participants complete the 24-week main treatment period to assess the safety and PK/PD, and exploratory efficacy of the results. The analysis will be executed with controlled dissemination to ensure the integrity of ongoing data collection while maintaining sufficient blinding in the study. The partial data of a participant's extended treatment period up until primary completion may be presented in separate tables. More details on the primary analysis are provided in the SAP. No formal interim report will be written.

The investigator, study staff, participants, monitors, members of the Sponsor's clinical operations team and CIAC will remain blinded until the end of the study.

The final data analysis will be conducted once all participants complete the follow-up period (the last participant's last follow-up visit). At the end of the study completion, statistical analysis will include all data, including the main treatment period, extension period, and the follow-up period appropriately.

07 JUL 2021 Page: 64 of 90

9.4.1 General considerations

9.4.1.1 Planned Methods of Analysis

Descriptive statistics will be provided by treatment group for all demographic variables, safety endpoints, and exploratory endpoints. The placebo groups from each cohort will be combined, so that there are four treatment groups to be included for analysis—40 mg, 80 mg, 120 mg, and placebo, all equal in size.

- The safety analysis set will be used for all safety endpoints, including the primary endpoint.
- The full analysis set will be used for the exploratory endpoints or otherwise specified.
- The PK analysis set will be used for the pharmacokinetic endpoints, and
- The PD analysis set will be used for the pharmacodynamics endpoints.

For categorical variables, frequencies and proportions will be provided by treatment group. For continuous variables, means, medians, standard deviations, standard error of mean, interquartile range (25th percentile, 75th percentile), and range (minimum, maximum) will be provided by treatment group. For continuous variables collected at multiple time points, the descriptive statistics will be provided at each time point.

All analyses and tabulations will be performed using SAS@ Version 9.2 or higher or if applicable, other software.

9.4.1.2 Incomplete or Missing Data

In general, missing data values will not be imputed. Incomplete data handling rules will be described in the specified section in the SAP if needed.

9.4.1.3 Inter-current event

The list of possible inter-current events identified in this study are:

- Unblinding to study intervention: the study allows unblinding of the treatment assignment if the investigator deemed it necessary related to a bleeding event or AE.
- Premature treatment discontinuation or kidney transplant or death
- Lowering high dose study intervention from 120 mg to either 100 mg or 80 mg based on DMC recommendation.

Other inter-current events will be described in the specified section where appropriate.

9.4.1.4 Demographic and Baseline characteristics

Demographic and baseline characteristics including dialysis and ESRD disease characteristics obtained before the first study intervention administration, e.g.;

- age, gender, ethnicity, race, weight, height, BMI,
- current hemodialysis characteristics,
- medical condition that most likely led to RRT,
- time since the start date for renal replacement therapy,

will be summarized using descriptive statistics by treatment group and all participants for full analysis set population and safety population.

07 JUL 2021 Page: 65 of 90

Age for each participant will be defined as the number of years between informed consent date and birth date.

For summarizing race, if multiple races are recorded in the database, then 'multiple race' will be used in the summary table.

The study sample sizes will be summarized by the trial unit (site) for enrolled participants. All participants with signed ICF will be included in the enrolled participants.

9.4.1.5 **Definition of Baseline**

Generally, measurements taken before first dose will be considered baseline values unless otherwise specified. For further details see the SAP.

9.4.1.6 On treatment

The "on-treatment" period is defined as the period between first administration of study intervention up to 28 days after the last administration of study intervention.

9.4.2 Primary endpoint(s)

The primary endpoint is the incidence of the composite of major bleeding and clinically-relevant non-major bleeding, as assessed by blinded CIAC.

Estimand for the primary safety endpoint:

The five attributes of the estimand are as follows:

- **Population:** ESRD patients as described by the inclusion/exclusion criteria given in Section 5.
- **Variable:** The incidence of composite of MB and CRNMB during the main treatment period, as assessed by CIAC.
- **Treatment:** Three dose groups of BAY 2976217 or placebo

• Intercurrent events:

- Unblinding to study intervention: the study allows unblinding of the intervention code: regardless of whether such an event occurs (treatmentpolicy strategy)
- Early definitive discontinuation of study treatment or death or kidney transplant: until the occurrence of the intercurrent event (while on-treatment strategy)
- Dose reduction: regardless of whether such an event occurs (treatment-policy strategy).
- **Population-level summary:** Proportion of subjects with a bleeding event by study intervention groups.

07 JUL 2021 Page: 66 of 90

The primary objective is to assess the safety of the three different doses of BAY 2976217 given once a month which is expected to be maintained during a chronic treatment. The primary safety analysis is based on a descriptive proportion of subjects with bleeding events based on the Safety analysis population. (see Section 9.3).

- All suspected events of bleeding will be reported as an AE or SAE as per adverse event reporting procedure in Section 8.3. Additionally, an adjudication package will be sent to the CIAC. The CIAC will classify bleeding as defined in Section 8.2.1.
- Proportion of subjects with bleeding events including the following categories will be tabulated by treatment as assessed by the CIAC:
 - Composite of MB and CRNMB
 - o MB
 - o CRNMB
 - o Minor bleeding
- For the primary safety analysis, primary safety outcomes will be considered during the main treatment period and while on-treatment. Incidences of MB, CRNMB, minor bleeding will be analyzed similarly.

The frequency and percentage of participants with bleeding will be reported where the denominator will be total number of participants in each treatment group in the safety analysis set. The corresponding exact binomial 95% confidence interval will be provided.

In addition, exposure adjusted bleeding rate analysis will be performed for the primary endpoint (for example, 100 person-years bleeding rate) and for the MB, CRNMB, minor bleeding, separately.

9.4.3 Secondary endpoints

- The incidence of composite of major bleeding and clinically-relevant non-major bleeding during the main and extended treatment periods and within the on-treatment time window. Similar additional analyses will also be done for MB, CRNMB, minor bleeding, separately.
- TEAE are defined as AEs that occurred or worsened after first dosing until 20 weeks after the last study intervention dose. For the primary analysis, TEAEs will be analyzed during the on-treatment time window within the main treatment period in the safety analysis set. In addition, TEAEs will be analyzed during the main and extended treatment periods and within the on-treatment time window. Results will be presented as incidence tables. All TEAEs, all TEAEs potentially related to study intervention, all TEAEs potentially related to ESRD, all TESAEs, and all TESAEs potentially related to study intervention (BAY 2976217 or placebo), TEAEs leading to early withdrawal of study intervention will be summarized by treatment group and by MedDRA preferred term and system organ class. Listings will be also provided.

07 JUL 2021 Page: 67 of 90

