Assuming 15% screen failure rate, approximately 340 participants will be screened to achieve an estimated total of 288 randomized participants, 96 per each cohort group and an estimated 80 participants per cohort after an assumed attrition rate of approximately 15%. Additional participants may be enrolled based on recommendations from the Steering Committee and/or DMC (e.g.- based on actual retention of participants, or other scientific or safety reasons).

07 JUL 2021 Page: 14 of 90

Intervention Groups and Duration:

Within each dose cohort, participants will be randomized in a 3:1 ratio to receive SC treatment with either BAY 2976217 or placebo. All standard of care hemodialysis therapies as prescribed by their providers, including use of heparins to maintain dialysis circuit patency, will be continued.

- Cohort A: 40 mg BAY 2976217 or placebo SC (3:1) n~96
- Cohort B: 80 mg BAY 2976217 or placebo SC (3:1) n~96
- Cohort C: 120 mg BAY 2976217 or placebo SC (3:1) n~96

Study intervention will be administered once every 4 weeks as described in the SoA, unless there is a need for dose interruption (Section 7.1). All cohorts will consist of 1-week screening period and a 24-week main treatment period, the last 4 weeks of which are an evaluation period for certain PD and safety parameters. To collect additional long-term safety information, participants will continue to be treated as randomized in the extended treatment period, with up to 24 weeks of additional treatment with study intervention. A participant is considered to be on treatment until 4 weeks after their last dose, whether they discontinue treatment early, complete only the main treatment period, or complete part or all the extended treatment period. Once the overall treatment period is completed, participants will have a 16-week post-treatment follow-up period, for a total of up to 65 weeks of participation.

All participants who are in the extended treatment period will need to stop treatment when the last participant enrolled into the study has completed the 24-week main treatment period (Visit 22). Participants in the extended treatment period will complete Visit 28 four weeks after their last dose, and move to the 16-week post-treatment follow-up period. The sponsor reserves the discretion to halt further dosing in the extended treatment period earlier in anticipation of the last participant completing the main treatment period.

Data Monitoring Committee: Yes

[figure not shown]

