All cohorts will consist of 1-week screening period and a 24-week main treatment period, the last 4 weeks of which are an evaluation period for certain PD and safety parameters. To collect additional long-term safety information, participants will continue to be treated as randomized in the extended treatment period, with up to 24 weeks of additional treatment with study intervention. A participant is considered to be on treatment until 4 weeks after their last dose, whether they discontinue treatment early, complete only the main treatment period, or complete part or all of the extended treatment period. Once the overall treatment period is completed, participants will have a 16-week post-treatment follow-up period.

07 JUL 2021 Page: 30 of 90

All participants who are in the extended treatment period will need to stop further treatment no later than when the last participant enrolled into the study has completed the 24-week main treatment period (Visit 22). Participants in the extended treatment period will complete Visit 28 four weeks after their last dose, and move to the 16-week post-treatment follow-up period. The sponsor reserves the discretion to halt further dosing in the extended treatment period earlier in anticipation of the least participant completing the main treatment period.

The data and outcomes collected in the study will be analyzed by 4 groups:

- Pooled Placebo Group (from Cohorts A, B and C),
- 40 mg Dose Group (BAY 2976217 from Cohort A),
- 80 mg Dose Group (BAY 2976217 from Cohort B), and
- 120 mg Dose Group (BAY 2976217 from Cohort C).

All suspected bleeding, cardiovascular and thromboembolic events occurring after randomization will be assessed by CIAC blinded to treatment allocation. An independent DMC will monitor the participant's safety and give recommendations to the Steering Committee.

The DMC will review unblinded data from the study on regular basis, as outlined in the DMC Charter. At any time, if there is an unexpected finding(s) in Cohort C (the 120 mg dose cohort), the DMC may elect to modify the Cohort C to a 100 mg or 80 mg dose level. If recommended by the DMC, the change will be implemented by administrative letter and will not require a protocol amendment. All ongoing participants will have their dosing modified to 100 mg or 80 mg once monthly and all new participants will be initiate dosing at 100 mg or 80 mg once monthly.

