4.5 Data Rules

4.5.1 Analysis Dates

For the study, the following date and time window are of relevance for the analysis:

• End of Study Date

The end of the study is defined as the date the last participant completes the last protocol-defined visit/contact.

• Primary Completion Date

The primary completion date is the date when the last participant completes the main treatment period . See the below period definitions for data collection in each period.

• Main Treatment Period (actual)

The main treatment period includes a total of 24 weeks

For subjects who *did not* enter the extension period the main treatment period is defined as the period from first dose of study intervention to the last date of dose +28 days.

For subjects who *did* enter the extension period the main treatment period is defined as the period from first dose of study intervention to the administration of study intervention (and hence commencement of the extension period), at visit 22.

• Extended Treatment Period (actual)

The extended treatment period includes a total of up to 24 weeks, from study intervention administration on visit 22 until the date of last dose +28 days or date of last contact (whichever comes first).

• Post-Treatment Follow-up Period (actual)

The post-treatment follow-up period includes a total of 16 weeks. For subjects who *did not* enter the extension period, the follow up is defined as the period from the end of the main treatment period +1 day to the last contact date.

For subjects who *did* enter the extension period, the follow up is defined as the period from the end of extension period + 1 day to the last contact date.

For each subject, the following individual dates are of relevance for analysis:

• Randomization date:

The date of randomization as recorded in the IxRS system.

• Date of the first dose of study intervention:

The date of the first dose of Fesomersen or placebo will be used from the appropriate eCRF page capturing the study intervention.

Date of the earliest logically possible dose of study intervention administration will be used, in cases where the date of the first dose is missing or incomplete.

• Date of the last dose of study intervention:

The date of the last dose of Fesomersen or placebo will be used from the appropriate eCRF page capturing the study intervention.

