6.4.3 Sensitivity and Supplementary Safety Analysis

To support the primary study results and to assess the robustness of the analysis, several additional sensitivity and supplementary analyses will be performed.

The primary safety endpoint will be analyzed using the same method described in Section 6.4.1.1 based on SAF analysis set and both TA and OA data scope.

In addition, analysis will be performed with additional bleeding events on SAF analysis set with PA data scope, and SAF analysis set with TA data scope:

- Minor bleeding
 - Minor bleeding will be further categorized as injection site and non-injection site bleeding events.

Additional analysis on the secondary safety endpoints will be performed based on SAF analysis set and TA data scope.

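### TEAEs over the main plus extended periods are reported only as crude percentages although possible treatment time varies with enrolment date; the exposure-adjusted rates already planned for bleeding should be added

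*Protocol*

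**What the plan says.** Protocol 4.1 offers an extension "with up to 24 weeks of additional treatment with study intervention", but those in it "will need to stop further treatment no later than when the last participant enrolled into the study has completed the 24-week main treatment period". The sponsor may halt dosing earlier. SAP 4.5.1 agrees: "The extended treatment period includes a total of up to 24 weeks, from study intervention administration on visit 22". A participant counts as on treatment until 28 days after the last dose (Protocol 9.4.1.6).

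TEAEs are a secondary endpoint in three windows: main period; main plus extended periods on treatment; and up to 20 weeks after the last dose (Protocol Table 3-1). For the second window Protocol 9.4.3 states: "TEAEs will be analyzed during the main and extended treatment periods and within the on-treatment time window. Results will be presented as incidence tables". SAP 6.4.2 describes counts and frequency tables by MedDRA class and term. SAP 6.4.3 extends them without a further method: "Additional analysis on the secondary safety endpoints will be performed based on SAF analysis set and TA data scope". SAP Table 5-2 labels this total-treatment (TA) scope additional and the overall (OA) scope exploratory.

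Exposure-adjusted rates are planned for bleeding (Protocol 9.4.2; SAP 6.4.1.1, carried to the TA and OA scopes by SAP 6.4.3) and for exploratory efficacy (SAP 6.2.1). Neither document plans them for TEAEs.

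**The concern.** The extension exists to gather longer-term safety data, yet its length is set by enrolment date and shortened further by discontinuation. A percentage with all treated participants in the denominator gives someone with 28 weeks of possible treatment the same weight as someone with 48, and treats time after early stopping as event-free. The figure therefore has no fixed time horizon, shifts with the speed of accrual, and is hard to set beside data from other studies. If one arm stops dosing more often for reasons unrelated to the event, its crude percentage also falls because there is less time in which to observe events.

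**Working it through.** 1. **The plan's own figures.** Maximum participation is 1 + 24 + 24 + 16 = 65 weeks, as the Synopsis states ("for a total of up to 65 weeks of participation"). With 15% dropout, 288 × 0.85 = 244.8 and 72 × 0.85 = 61.2, close to the stated 240 completers and 60 per group (Protocol 9.2).

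2. **Treatment time after a calendar stop.** In Protocol Table 1-3 the last extension dose is at Visit 27 (Week 45, Day 309) and Visit 28 is Day 337; 309 + 28 = 337. The rule stops dosing, and on-treatment time runs 28 days beyond the last dose. A participant therefore gets the full 48 weeks if Visit 27 falls on or before the stop, that is, if at least 45 − 25 = 20 weeks separate their own Visit 22 (Week 25) from it. With a weeks between the two, dosing at Visit 22 and every 4 weeks, possible on-treatment time is L = 24 + 4 × (floor(a/4) + 1), capped at 48: 28, 32, 36, 40, 44 or 48 weeks.

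3. **Share short of 48 weeks.** No accrual period is given. Assume uniform accrual over A weeks, a stop exactly at the last Visit 22, and no attrition. The share is 20/A.

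| A (weeks) | 26 | 39 | 52 | 78 | 104 |
|---|---|---|---|---|---|
| 20/A | 77% | 51% | 38% | 26% | 19% |

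4. **Crude TA incidence.** Assume a TEAE with 5% risk per 24 weeks and a constant hazard. Risk by L weeks is 1 − 0.95^(L/24), so the 48-week risk is 1 − 0.95² = 9.75%. For L = 28, 32, 36, 40 and 44 the risks are 5.81%, 6.61%, 7.41%, 8.19% and 8.98%, summing to 36.99%. Each of these five bands has probability 4/A, so

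   crude incidence = (4/A) × 36.99% + (1 − 20/A) × 9.75%.

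   - A = 26: 5.69 + 2.25 = 7.9%, which is 19% below 9.75%.
   - A = 39: 3.79 + 4.75 = 8.5%, 12% below.
   - A = 52: 2.85 + 6.00 = 8.8%, 9% below.

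5. **Unequal discontinuation, A = 52.** Suppose a share d stops at times uniform over the first 24 weeks, independently of the event, and has no extension. With hazard λ = −ln(0.95)/24, the mean risk of stoppers is 1 − 0.05/0.0513 = 2.52%. Crude incidence is d × 2.52% + (1 − d) × 8.85%: 7.90% at d = 15% (the plan's dropout figure, used here for placebo), 7.58% at 20%, 7.26% at 25% and 6.95% at 30%. The last three are assumptions for an active arm. With the same hazard in both arms the risk ratios are 0.96, 0.92 and 0.88. Under a constant hazard and stopping unrelated to the event, a person-time rate ratio would be 1.00 in each case.

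The OA scope inherits the same spread in treatment time, with post-treatment follow-up added. No separate figure was worked for it.

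**The case against.** Several objections are sound. Randomisation to the arms is concurrent, so the calendar stop shortens exposure alike in all of them; a reader might infer that it distorts the contrast with placebo, and it does not. A reader might also equate the dosing stop with the end of on-treatment time and take the share short of 48 weeks as 24/A (46% at A = 52). The 28-day window makes it 20/A (38%).

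The discontinuation effect rests on assumed stopping rates: the documents give only about 15% overall. Even at 30%, the gap in step 5 is 0.95 percentage points, or 72 × 0.0095 ≈ 0.7 of a participant per group, in a study with no planned hypothesis test for its sizing. The calculation also needs stopping to be unrelated to the event. Participants stopped by the platelet or liver rules have already met an AESI threshold and are in the numerator, so the effect does not apply to those AESIs. A reader might infer that a higher dose will look safer than it is. Dose-dependent platelet decreases were seen with the parent compound, but no platelet reductions were seen with this compound in healthy volunteers (Protocol Table 2-1), so unequal stopping is possible, not established.

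The plan also has partial safeguards. The main TEAE analysis uses the main period. Treatment duration is summarised by group (SAP 6.1.7), withdrawal patterns are compared (SAP 4.3), event counts accompany participant counts (SAP 6.4.2), and early stoppers remain in follow-up. But none of these links events to time at risk, and the open-ended top duration category starts at about 24 weeks, so it does not separate short from full extensions. The sentence in SAP 6 on incidence rates sets only a minimum-event condition. The separate table specifications could add rates; neither document commits to them.

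**Conclusion.** The point holds as a reporting gap in an additional descriptive analysis. Possible treatment time varies with enrolment date, and the TA and OA tables for TEAEs carry no person-time measure, although the SAP uses one for bleeding and exploratory efficacy. Assuming uniform accrual over 26 to 104 weeks and a stop exactly at the last Visit 22, 77% to 19% of participants cannot have 48 weeks on treatment; an earlier halt would raise these shares. For the illustrative TEAE, the crude figure understates the 48-week risk by about 19% (A = 26) to 9% (A = 52), before attrition and under a constant hazard.

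Bias in the contrast with placebo is conditional: it needs unequal stopping that is unrelated to the event. A reader might go further and doubt the primary endpoint or Phase 3 dose selection. The documents do not support that: the primary analysis, which serves dose selection, follows completion of the main period by all participants, and the primary endpoint and main TEAE analysis are confined to that period. This is a cheap improvement.

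**What to change.** In Protocol 9.4.3 and SAP 6.4.2/6.4.3, for the TA and OA scopes, add an exposure-adjusted incidence rate per 100 participant-years beside the crude percentages for at least overall TEAEs, TESAEs, study-drug-related TEAEs and AESIs. Define it as participants with a first event divided by summed time from first dose to that event or the end of the scope, by treatment group, with the 90% chi-square interval already given in SAP 6.4.1.1. Label the crude TA percentage as covering variable possible treatment of up to 48 weeks.

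The cost is SAP wording and extra table columns; the dates are already collected. SAP 6.5 indicates that the primary analysis was already complete, so the change would apply to the final analysis, which includes all extension and follow-up data. The downsides are longer tables and the constant-hazard reading of a rate: for events concentrated early in treatment, the rate itself falls as exposure lengthens, so the crude percentage should stay alongside it. The primary endpoint and the main-period TEAE analysis need no change.
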